3.3.0 Exploratory outcome measures

3.3.1 Change in rating of BPSD - calculated by the difference in NPI-Q total scores (baseline, 3-mo, 6-mo). The intervention group will be compared to the control group for the same time intervals.

3.3.2 Change in caregiver distress - calculated by the difference in NPI-Q caregiver distress total scores (baseline, 3-mo, 6-mo). The intervention group will be compared to the control group during the same time intervals.

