6.2 Preliminary Work: Neuropsychiatric Inventory Questionnaire (NPI-Q) –

Ecological Momentary Assessment (EMA) Caregiver Pilot: We successfully pilot tested the NPIQ-EMA app in four AD patient-caregiver dyads without any attrition. The time horizon for the pilot differs from the proposal in that the caregiver was asked to fill out the smartphone survey (NPIQ-EMA) daily for a 2-week time period. Patient ages ranged from 63 to 95, and caregiver ages ranged from 63 – 82. Three of four caregivers identified as African American. All four caregivers found answering the NPIQ-EMA questions to “Not be burdensome.” Several caregivers reported that the NPIQ-EMA improved their awareness of the patient’s BPSD. Three of four answered that they would prefer weekly monitoring rather than daily and the last caregiver expressed a preference for daily monitoring. All caregivers agreed that the system was easy to use.

6.3 Recruitment, Screening, Informed Consent, and Enrollment: The Sandra Eskenazi Center for Brain Care Innovation provides longitudinal care to ~ 600 patients; 38.7% are Black; and 70.4% are female. In addition, each of five clinicians completes an initial assessment on 1-3 new patients per week. We anticipate a recruitment number of 154 dyads over 27 months and believe this to be achievable. Half of the dyads would be randomized to the intervention or treatment as usual group. Our group has a recruitment rate of approximately 50% of eligible subjects in this environment⁴³.

6.4 Randomization Scheme: Participating dyads will be randomized to the two groups (intervention vs control) using a randomization list that contains group assignment in blocks, thus ensuring that the groups have comparable sample sizes throughout the study. We will use a stratified block random assignment following the Kernan strata determination formula (Kernan et al. 1999) listed as, $\# \text{ of strata} < n / B \times 4$, where B is block size and “... n is the sample size at the first planned interim analysis and 4 is a safety factor that accounts for unequal distribution of patients among strata.” Using $n=154$ and $B=4$, then, the $\# \text{ of strata} < 9$. In this study, we will use 8 strata = 2 Diagnosis (aMCI, AD) x 2 Gender (M, F) x Age (< 65, \geq 65). Sealed envelopes with randomization assignments will be prepared by a research team member not involved

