- The informed consent document and HIPAA authorization form will be reviewed over the telephone, rather than in-person, to minimize COVID-19 exposure. Once the participants have had time to ask questions and their understanding of the study is assessed, verbal consent will be attained. At this point in time, the study team member will ask the caregiver their appointment type preference, whether they want to meet in person the Eskenazi Health, Fifth Third Building or complete the assessments over the phone.
- Before verbal consent is obtained, the patient will be assessed to determine their capacity to consent to research.
 - The provider reports the patient lacks the capacity to consent.
 - The MMSE score is ≤ 17
 - If neither of the aforementioned measures have been met, the study team will ask the patient the following 4 questions:
 - What do you understand is wrong with your brain health right now?
 - Can you please explain in your own words the choices I have presented to you (choice to consent)?
 - If you decide to participate in this study, what good things might happen and what harm might occur?
 - Can you please explain how you decided to participate (or not participate) in this study?
 - The determination to have the capacity to consent to research the patient must answer these 4 questions correctly.
 - The patient's Legal Authorized Representative (LAR) will consent on the patient's behalf if any of the following conditions are met:
 - The patient lacks the capacity to consent to research.
 - The patient is unable to communicate verbally or through another method due to the progression of their disease.
 - The patient has a court appointed guardian.

As a part of the informed consent process, once capacity to consent has been established, the study team member will ask four teach back questions related to the study to both the caregiver and the patient. These questions are asked to ensure the caregiver and patient understand what they are consenting to, as well as making them aware that we have safety procedures in place to minimize their exposure to COVID-19.

 - If the caregiver chooses to complete the assessments remotely, the study team member will schedule a time to deliver study supplies. Regardless of what

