randomization group they are in, the study team member will deliver a plastic bin which contains a binder with paper copies of the assessments and other study related materials. It will be delivered to the patient and caregiver's respective homes without direct contact from team members (left outside home). If the dyad has been randomized to Group 2- The Three Assessments and Mobile Application and request to use a study mobile phone, this will be included in the plastic bin. The purpose of the study binder is to ensure the dyad is able to follow along during the assessment. The study team members will have a mirror binder where they will indicate the caregiver's responses to the assessment questions.

- The study team member will then arrange a time for the caregiver to complete the baseline study visit. The baseline study visit will be completed over the telephone or if the caregiver prefers in-person at the Eskenazi Health, Fifth Third Building located on the Eskenazi Health Hospital Campus (the in-person visit is entirely optional).
- The patient will not be present or participate in the baseline, 3-month or Final / 6-month research visit.
 - During the informed consent visit, patients who have the capacity to consent will consent to the HIPAA authorization form, which grants the study team permission to access their Eskenazi Health medical record and to communicate with their SECBCI clinical team. If they do not have the capacity to consent, then their LAR will consent on their behalf.
 - The caregiver will also be asked to consent to a HIPAA authorization form as some of the assessments address their own personal health. In addition they will agree that data collected by the research team can be used for the purposes of research.
- If consent by LAR is necessary, the study team will also seek a separate assent to participate from the individual with aMCI or AD. If an assent isn't obtained, an audible dissent will be honored.
- The patient with aMCI or AD will not receive any assessment or participate in interviews as their participation in the study is passive. Once enrollment of the patient with aMCI or AD is complete, they have completed their portion of the study. All other activities will involve the caregiver or the caregiver monitoring the patient with aMCI or AD.

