Analysis H3: The change in rating of BPSD calculated by the difference in NPI-Q total scores and caregiver distress calculated by the difference in NPI-Q caregiver distress total scores at time of baseline assessment, 3 months and 6 months of the intervention group will be compared to the control group during the same time intervals. For this comparison we will use a between-group test, using mixed linear models to adjust for baseline covariates and to adjust for the baseline measure of the response variable (i.e., baseline NPI-Q total score or NPI-Q caregiver distress total score), will be used to compare the intervention group and control group on the repeated measured follow-up response variables (i.e., follow-up NPI-Q total score or NPI-Q caregiver distress total score). Separate models will be run for the NPI-Q total score and NPI-Q caregiver distress total score. A within-group test, using mixed *linear* models to adjust for baseline covariates and to adjust for the baseline measure of the response variable (i.e., baseline NPI-Q total score or NPI-Q caregiver distress total score) as well as the period effect (i.e., months 1-6) and the randomized condition (i.e., assigned to start with weekly vs monthly surveillance frequency), will be used to compare the two surveillance conditions (measured weekly or monthly depending on the month period) within the intervention group in a 2 x 6 cross-over analysis. We will also use these *linear* mixed models to perform the same type of between-group and within-group analyses in which the dependent variables are the following secondary variables: Perceived Stress Scale-14, and Zarit Burden Interview.

12.4 Power Justification and Analysis: The study was designed to have a power of 80% for two-tailed tests with a significance of 5%.

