16.0 Other

16.1 Essential Equipment: We will use the Android Pixel phone by Google as a loaner phone for study subjects (caregivers) who do not have their own smartphone. The phone will be pre-loaded with the EMA version of the NPI-Q delivered by mobile app.

16.2 Potential Problems and Alternative Strategies:

16.2.1 Worsening caregiver burden: One concern of this proposal, is whether EMA monitoring of BPSD creates too much of a burden on the already burdened caregiver. Participants in our 28-day R01 study and in our pilot have not found the EMA pinging of the smartphone to be burdensome. The R01 study population demographics overlap significantly with our anticipated patient-caregiver population. As a safeguard, we will use usability and burden questions from the semi-structured interview from the initial 10 aMCI/AD caregiver-dyads to determine if the burden of answering EMA questions for the caregivers is too great. If that does turn out to be the case we will consider lengthening the surveillance interval or shortening the assessment battery.

16.2.2 Drop off in participation during the monthly response interval: It is possible that participation in the EMA BPSD surveillance might drop off during the two-month block, where BPSD surveillance takes place monthly instead of weekly. To address the potential, drop off in participation during the monthly surveillance block we will observe attrition rates for our first 10 dyads. If attrition rates exceed that of 17% we will make an adjustment to surveillance frequencies dropping the monthly surveillance block and instead continuing with weekly surveillance.

16.3 Summary and Future Directions: The following study looks to improve the care of aMCI/AD patient-caregiver dyads through the study of a BPSD surveillance intervention. Our choice of a weekly/monthly frequency, was a conservative approach in this early work to manage caregiver and provider burden but should evidence indicate high feasibility and value of weekly intervals, a future project could test higher frequencies to identify a frequency of diminishing return. Findings from this study will be used to develop a BPSD surveillance EMA intervention for a future R01 proposal that will improve the access to care and health of AD patient-caregiver dyads. This work will help my maturation into an independently funded investigator.

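### Remote dyads are allocated before the caregiver-rated baseline, so arm knowledge could bias the between-group Aim 3 comparisons

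*Combined protocol and SAP*

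**What the plan says.** Section 7.0 describes the remote route in sequence. After telephone consent, "If the caregiver chooses to complete the assessments remotely, the study team member will schedule a time to deliver study supplies". Every remote dyad then receives a bin with a binder of paper assessments, whichever group it is in. "If the dyad has been randomized to Group 2- The Three Assessments and Mobile Application and request to use a study mobile phone", the phone goes in the same bin. On the binder: "The purpose of the study binder is to ensure the dyad is able to follow along during the assessment". The next step is: "The study team member will then arrange a time for the caregiver to complete the baseline study visit". The baseline NPI-Q, PSS-14 and ZBI are collected at that visit, and a team member records the caregiver's answers in a matching binder.

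Section 16.1 describes the device as a "loaner phone for study subjects (caregivers) who do not have their own smartphone". Section 6.4 covers envelope preparation ("Sealed envelopes with randomization assignments will be prepared by a research team member not involved" with enrolment) but gives no opening time relative to baseline.

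For change in NPI-Q total, 3.3.0 says: "The intervention group will be compared to the control group for the same time intervals". The Aim 3 models in 12.3 "adjust for the baseline measure of the response variable". Section 12.3 applies the same models to PSS-14 and ZBI, which it calls secondary variables.

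**The concern.** The Aim 3 outcomes are subjective caregiver reports in an open trial. A baseline rated after the caregiver knows the arm is no longer a pre-randomisation measurement. A caregiver who has just been handed the monitoring phone may report more symptoms or distress than otherwise, or fewer. The arms would then differ at baseline for reasons other than chance.

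Adjusting for baseline does not cure this, because allocation has influenced the covariate itself. Over-reporting at baseline in the app arm would look like later improvement, and under-reporting would hide a benefit. Section 1.0 says these impact data are meant to support an application for a fully powered trial, so a spurious or masked difference would carry forward.

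**Working it through.** **Order of events.** Section 7.0 speaks of randomisation as already done when the bin is packed. Three points indicate that the bin arrives before the baseline ratings:
- the binder is for following the assessment;
- Section 7.0 describes supply-box delivery and retrieval for remote assessments, baseline included;
- Table 4 (Section 8.0) places app installation, on a loaner or own phone, at the baseline visit.

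**Who can know the arm.** Caregiver knowledge is shown for one subset only: remote, app arm, loaner phone. Staff who pack the bin also know, and nothing separates them from whoever records the answers. For controls, own-phone users and in-person dyads, the text does not say when the arm is revealed.

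**The plan's figure (12.4).** With 64 per arm, d = 0.50 and two-sided 0.05, t-test power is 80.1%. Enrolment is 128/0.83 = 154.2, stated as 154. Both reproduce, and neither depends on when baseline is taken.

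**Inputs for the illustration.** From the plan: 64 per arm and a 0.50 SD design effect. Assumed, because the documents give none of them:
- reported baseline shift s = 0.1–0.3 SD, absent at follow-up;
- baseline-to-follow-up slope r = 0.5–0.7, with SD 1;
- share f of app-arm dyads affected = 10%, 25% or 50% (about 6, 16 or 32 of 64).

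**Bias.** Adjusted difference = follow-up difference − r × baseline difference, so the shift contributes r·s·f in absolute size. A plain change score carries s·f.

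**Type I error.** For one follow-up score, SE = √(2/64) × √(1 − r²): 0.153 at r = 0.5 and 0.126 at r = 0.7. The two-sided error is Φ(bias/SE − 1.96) + Φ(−bias/SE − 1.96).

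| f | r·s·f, lowest to highest (SD) | Share of 0.50 SD | Type I error, lowest to highest | s·f (SD) |
|---|---|---|---|---|
| 10% | 0.5×0.1×0.10 = 0.005 to 0.7×0.3×0.10 = 0.021 | 1.0–4.2% | 5.0–5.3% | 0.010–0.030 |
| 25% | 0.0125 to 0.0525 | 2.5–10.5% | 5.1–7.0% | 0.025–0.075 |
| 50% | 0.025 to 0.105 | 5–21% | 5.3–13.2% | 0.050–0.150 |

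For the largest entry, 0.105/0.126 = 0.83, which gives 13.2%. Simulating 20,000 trials at r = 0.7 and s = 0.3 gave type I errors of 5.2%, 6.9% and 12.8% for the three shares. If the 3- and 6-month scores are averaged with a common correlation of 0.7, the SE falls to 0.106 and the simulated errors are 5.4%, 7.4% and 15.9%.

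**If the shift persists.** Suppose the whole app arm also reports s higher (or lower) at follow-up. A clean baseline then leaves the full s, 0.1–0.3 SD. The present order leaves s × (1 − r·f). The offset r·f is 5–7% at f = 10%, 12.5–17.5% at 25% and 25–35% at 50%.

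**The case against.** The order is inferred from a logistics paragraph. Figure 1 is not shown and the Manual of Procedures is not supplied; either may state when envelopes are opened. Caregiver knowledge is shown only for a narrow subset. The ratings are the caregiver's own answers, so staff knowledge is a weaker route, and the illustration does not model it. At the midpoints s = 0.2 and r = 0.6, type I error is 5.1%, 5.5% and 7.1% for the three shares, so 13% is an extreme corner. A clean baseline also leaves open-label reporting at 3 and 6 months untouched, and that may be the larger bias. PSS-14 and ZBI are not listed under Secondary outcome measures (3.2.0), which names only actionable data.

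Most of this stands as a limit on size and reach. It does not remove the point. A Figure 1 or Manual with the opposite order would conflict with Section 7.0, and the text would still need correcting. Partial cancellation of two biases of unknown size is not a safeguard. The label for PSS-14 and ZBI is 12.3's own; the actionable-data outcome is not part of this concern.

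**Conclusion.** The concern holds. Followed as written, Section 7.0 gives remotely assessed dyads a post-allocation baseline, and the arm can be known before rating by app-arm caregivers sent a loaner phone and by the staff who pack it. This could bias the between-group Aim 3 comparisons of NPI-Q total and distress (exploratory) and of PSS-14 and ZBI.

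The direction is unknown. The illustrated adjusted bias runs from a negligible 0.005 SD to 0.105 SD, and rests entirely on the assumed s, r and f. Confidence is medium because two sources that may fix the timing could not be seen. The change should be made, but the trial's primary feasibility results do not depend on it.

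**What to change.** - In 6.4, state that the envelope is opened only after the baseline NPI-Q, PSS-14 and ZBI and the pre-intervention interview are completed and recorded.
- In 7.0, make the first bin identical for all remote dyads, with loaner delivery and app installation afterwards.
- Give one order of consent, baseline, randomisation and app set-up for both visit types. As a minor related point, 7.0 puts consent before the baseline visit, while Table 4 and Section 14.0 put it at that visit.

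The cost is procedural wording, a second drop-off for remote app-arm dyads who need a loaner phone, and slightly later app set-up. Sample size and power are unchanged. The change protects the baseline only: if the same reporting shift persists at 3 and 6 months, a clean baseline will show it in full. If Figure 1 or the Manual already has this order, only the text of 7.0 needs correcting.

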8.0 Study Calendar

A detailed table of study activities is listed below.

Table 4. Schedule of Study Activities

Schedule of Study Activities	Baseline Visit Within 14 days of enrollment	3-mo Within 14 days of scheduled target date	Final Visit (6-mo) Within 14 days of scheduled end
Provision of Study Information	X		
Completion of Informed Consent and HIPAA Consent	X		
Installation of BCN on loaner or caregiver phone	X		
Provision of BCN instructions	X		
Provision of Education on BPSD	X	X	X
COVID-19 Symptom Screener	X	X	X
Collect/Administer the following:			
COVID-19 Physical & Mental Health Questionnaire	X	X	X
Single Item Literacy Screener (SILS)	X		
Dyad Demographics	X		
NPI-Q	X	X	X
PSS-14	X	X	X
ZBI	X	X	X
Motivators and Barriers Survey	X		
Caregiver Pre-Intervention and Phone Semi-Structured Interview*	X	X	X
Caregiver & Environment Assessment of Neuropsychiatric Symptoms (CEAN)*	X	X	X
BCN app - Task Completion Burden Questions*	X	X	X
BCN app - Free Response Follow-Up Questions*	X	X	X
Data from EMR	X	X	X
Senior Technology Acceptance Scale	X	X	X

System Usability Scale (SUS)		X Intervention group only	X Intervention group only
Caregiver Post-intervention Survey		X Intervention group only	X Intervention group only
Caregiver Post-Intervention Semi-Structured Interview			X
Loaner phone retrieved or BCN app uninstalled from the caregiver phone			X
Provision of a \$10 Kroeger gift card to Caregiver	X		X
Provision of a \$10 Kroeger gift card to Caregiver	X		
Provision of a parking voucher, only if visit is conducted in-person	X	X	X

* Triggered by Clinically Significant BPSD

9.0 Collection and Reporting of Adverse Events and Serious Adverse Events

The PI will comply with Indiana University IRB and the NIA guidelines for defining, collecting, and reporting serious adverse events (SAE), adverse events (AE), and unanticipated problems.

9.1 AE/SAE Definitions

9.1.1 Classification of Severity, Expectedness and Study Relatedness

Severity

- **Mild** - Awareness of signs or symptoms, but easily tolerated and are of minor irritant type causing no loss of time from normal activities. Symptoms do not require therapy or a medical evaluation; signs and symptoms are transient.
- **Moderate** - Events introduce a low level of inconvenience or concern to the participant and may interfere with daily activities, but are usually improved by simple therapeutic measures; moderate experiences may cause some interference with functioning
- **Severe** - Events interrupt the participant's normal daily activities and generally require systemic drug therapy or other treatment; they are usually incapacitating

Expectedness

AEs will be assessed as to whether they were expected to occur or unexpected, meaning not anticipated based on current knowledge found in the protocol, investigator brochure, product insert, or label.

Categories

- **Unexpected** - *nature or severity of the event is not consistent with information about the condition under study or intervention in the protocol, consent form, product brochure, or investigator brochure.*

- **Expected** - event is known to be associated with the intervention or condition under study.

Relatedness

The potential event relationship to the study intervention and/or participation is assessed by the PI with input from the study research coordinator.

Categories

- **Definitely Related** - The adverse event is clearly related to the investigational agent/procedure – i.e. an event that follows a reasonable temporal sequence from administration of the study intervention, follows a known or expected response pattern to the suspected intervention, that is confirmed by improvement on stopping and reappearance of the event on repeated exposure and that could not be reasonably explained by the known characteristics of the subject's clinical state.
- **Possibly Related**: - An adverse event that follows a reasonable temporal sequence from administration of the study intervention follows a known or expected response pattern to the suspected intervention, but that could readily have been produced by a number of other factors.
- **Not Related**: - The adverse event is clearly not related to the investigational agent/procedure - i.e. another cause of the event is most plausible; and/or a clinically plausible temporal sequence is inconsistent with the onset of the event and the study intervention and/or a causal relationship is considered biologically implausible.

